4.2 Study Treatments

As previously described, the starting dose of 30 mg for SAD Cohort A1 is based on nonclinical safety findings and regulatory guidelines for selection of starting doses for FIH studies (see [Section 2.3.1](#)). For all subsequent parts of the study described below, the decision to enroll a cohort and its dose level and once daily (QD) or twice daily (BID) dosing schedule will be based on the assessment of available data, and some prespecified cohorts may not be enrolled.

4.2.1 Part A (SAD in Healthy Subjects)

- Cohort A1: 30 mg ABI-4334 or PBO, orally (PO), single dose, fasted
- Cohort A2: to be determined (TBD) mg ABI-4334 or PBO, PO, single dose, fasted
- Cohort A3: TBD mg ABI-4334 or PBO, PO, single dose, fasted
- Cohort A4: TBD mg ABI-4334 or PBO, PO, single dose, fasted
- Cohort A5: TBD mg ABI-4334 or PBO, PO, single dose, fasted
- Cohort A6: Food effect cohort with subjects from a previous fasted cohort, TBD mg ABI-4334 or PBO, PO, single dose, fed
- Cohort A7: Additional food effect cohort (if needed), TBD mg ABI-4334, PO, single dose, 2-period crossover (fasted & fed)

4.2.2 Part B (MAD in Healthy Subjects: 8-Day Dosing Duration)

- Cohort B1: TBD mg ABI-4334 or PBO, PO, multiple doses

- Cohort B2: TBD mg ABI-4334 or PBO, PO, multiple doses

For detailed information regarding dosing and administration, refer to [Section 6.1.1.4](#).

4.3 Duration of Treatment

The duration of treatment for each part of the study is provided below:

- Part A (SAD): 1 day
- Part B (MAD): 8 days

4.4 Duration of Study

- Part A (SAD): Up to 36 days per cohort, including 28 days of screening, 1 day of treatment, 7 days of follow up. The duration of the study will be longer for subjects in the food effect cohort(s).
- Part B (MAD): Up to 43 days, including 28 days of screening, 8 days of treatment, and 7 days of follow up.

4.5 End of Study Definition

For each subject, EOS is defined as completion of the last visit in the follow-up period or premature study termination, or subject is lost-to-follow-up.

The study will end when the last subject completes the last visit of the follow-up period or is considered “lost to follow-up,” whichever is later.

5 STUDY POPULATION

5.1 Number of Subjects

- Part A: Up to 46 (approximately 8 subjects/Cohorts A1-A6; 6 subjects/Cohort A7 [Note: Cohort A6 will enroll returning subjects from a previous SAD cohort])
- Part B: Up to 16 (approximately 8 subjects/cohort)

5.2 Inclusion Criteria

Subjects must meet all of the following inclusion criteria in order to be eligible for the study:

1. Is willing and able to provide informed consent prior to Screening.
2. Male or female ≥ 18 and ≤ 65 years of age at Screening.
3. Subject has a body mass index (BMI) between 18.0 and 30.0 kg/m² (inclusive) at Screening.
4. Subject is in good health (as determined by the Investigator) based on medical history, physical examination, 12-lead electrocardiogram (ECG), and clinical laboratory results. Medical history and physical examination must be without major or clinically significant findings.
5. Subject has serum chemistry (fasting), hematology, coagulation, and urinalysis values within reference range or has values outside the reference range, which are deemed not clinically significant deviations from the reference range, during the screening period (as determined by the Investigator).
6. Female subjects of childbearing potential (defined in [Appendix 5](#)) must be nonpregnant and have a negative serum pregnancy test at Screening and Day-1 and a negative urine pregnancy test on Day 1, obtained prior to dosing.
7. Agreement to comply with protocol-specified contraceptive requirements ([Appendix 5](#)).
8. Male subjects must agree not to donate sperm from Screening through at least 90 days after administration of the last dose of study drug ([Appendix 5](#)).

5.3 Exclusion Criteria

Subjects who meet any of the following exclusion criteria will not be eligible for the study:

1. Subject has positive results for any of the following serology tests: HBsAg, hepatitis B core antibody (HBcAb IgM), hepatitis C virus antibody (HCV Ab), or HIV-1 or -2 antibody.
2. Females who are pregnant, lactating, or wish to become pregnant during the course of the study.
3. Subject has a history of any illness that, in the opinion of the Investigator, might confound the results of the study, pose an additional risk in administering study drug to the subject, or a condition known to interfere with the absorption/distribution/elimination of drugs. This may include, but is not limited to, a history of relevant food allergies, history of cardiovascular or

central nervous system disease, history or presence of clinically significant pathology, or history of mental disease.

4. Subject has a history of malignancy in the last 5 years, with the exception of nonmetastatic basal cell or squamous cell carcinoma of the skin or localized carcinoma of the cervix.
5. Subject has had an illness within 5 days before receiving the first dose of study drug (“illness” is defined as a recent nonserious, nonacute condition such as the flu or the common cold).
6. Subject has hypersensitivity or history of idiosyncratic reaction to any components or excipients of the study drug (ABI-4334 or PBO).
7. Subject has a history of any significant (as determined by the Investigator) drug-related allergic reactions such as anaphylaxis, Stevens-Johnson syndrome, urticaria, or multiple drug allergies.
8. Subject has a history of persistent alcohol abuse (alcohol consumption exceeding 2 standard drinks per day on average [1 standard drink=14 grams of alcohol]) or illicit substance/drug use within 3 years prior to Screening.
9. Unwillingness to abstain from the use of marijuana from Screening through end of study.
10. Unwillingness to abstain from alcoholic beverage consumption 48 hours prior to Day 1 dosing through end of study.
11. Unwillingness to abstain from consumption of grapefruit, pomelo, or Seville oranges whole fruits or juices for 7 days prior to Day 1 dosing through end of study.
12. Subject has a smoking habit, uses, or has used tobacco or nicotine-containing products (eg, including but not limited to cigarettes, e-cigarettes, pipes, cigars, chewing tobacco, nicotine patches, nicotine lozenges, or nicotine gum) within 3 months before Day 1 dosing AND is unwilling to abstain from tobacco or nicotine-containing products through end of study.
13. Unwillingness to abstain from caffeine in any form, including tea, cola, and caffeinated beverages consumption 48 hours prior to Day 1 dosing through end of study.
14. Subject must be willing to stop herbal/dietary supplements (eg, vitamins, St. John’s Wort, ginkgo biloba, garlic supplements), over-the-counter (OTC) medications (except for paracetamol), or any prescription medication beginning 14 days prior to the Day 1 dosing or 5 half-lives, whichever is longer, and through end of study.
15. Subject has participated in a clinical study involving administration of either an investigational or a marketed drug within 2 months or 5 half-lives (whichever is longer) before Screening.
16. Subject has donated or lost more than 1 unit of blood (500 mL) within 60 days prior to Screening, or plasma donation within 7 days prior to Screening, or plans to donate blood or plasma during the study.

5.4 Screen Failures

Screen failures are defined as subjects who sign the Informed Consent Form (ICF), are assigned a subject number, complete screening procedures but are not subsequently randomized to study

treatment. Minimal information to be retained on all screen failures includes demography, screen failure details, eligibility criteria, and any SAE information.

Individuals who do not meet the protocol eligibility criteria for participation in this study (screen failure) may be allowed to rescreen (once). Rescreening may occur following resolution of acute exclusionary conditions or stabilization of conditions that were exclusionary and reversible (eg, unstable hypothyroidism, electrolyte abnormalities) and with the approval of the study Medical Monitor.

A single retest for a laboratory parameter(s) is permitted if there is a specific issue related to the collection, shipping, processing or analysis of a sample (eg, receipt of a hemolyzed sample at the testing laboratory, or samples received by the testing laboratory outside of the acceptable time window or temperature range) or related to a resolved condition.

If more than 28 days are required to obtain a result of a screening procedure and/or test conducted within the permitted window, the screening period may be extended until results are obtained. However, the clinical safety laboratory tests may need to be repeated under the instruction of the study Medical Monitor if the screening period is beyond 28 days.

5.5 Dietary and Lifestyle Restrictions

Subjects will be required to comply with the following restrictions during study participation:

- Subjects will not engage in strenuous exercise beyond their accustomed daily level of activity from Day 1 dosing through end of study.
- Subjects are prohibited from illicit substance/drug use and the use of marijuana before dosing on Day 1 through end of study.
- Subjects are prohibited from consuming any amount of alcohol 48 hours before dosing on Day 1 through end of study.
- Subjects are prohibited from nicotine consumption from Screening through end of study.
- Subjects are prohibited from consuming caffeine in any form, including tea, cola, and caffeinated beverages 48 hours before dosing on Day 1 through end of study.
- Subjects are prohibited from consuming grapefruit, pomelo, or Seville orange whole fruits or juice for 7 days before dosing on Day 1 through end of study.
- Subjects will be advised to take measures to minimize exposure to ultraviolet light from Day 1 through 7 days after the last dose of study drug, as an initial assessment for the potential for phototoxicity has not yet been conducted.

- Subjects who are women of childbearing potential should not plan to become pregnant during the study and all subjects should adhere to the contraception guidelines specified in [Appendix 5](#).
- Subjects must be fasting for at least 8 hours before chemistry assessments (Note fasting requirements for assessment of PK are provided in [Sections 6.1.1.4.1](#) and [6.1.1.4.2](#)).

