4.1.1 Part A (SAD in Healthy Subjects)

Part A of the study will enroll up to 5 fasted cohorts, ie, Cohorts A1-A5, and up to 2 fed cohorts to evaluate food effect, ie, Cohort A6 (with subjects from a previous fasted cohort), and an additional cohort, ie, Cohort A7, if needed (with new subjects).

The first cohort of Part A, ie, Cohort A1, will evaluate a single dose of 30 mg ABI-4334 ([Figure 2](#)). Dose levels for subsequent cohorts will be determined based on interim cohort review performed by an unblinded DRC (see [Section 10.6](#) for details on DRC procedures) between SAD cohorts for purposes of dose escalation. Study data will include safety data from Day 1 through Day 4 for the present cohort and all available safety data for preceding cohorts. In addition, PK

data through 24 hours after dosing for the present cohort and available PK data for preceding cohorts will be reviewed. In no case would a dose escalation be greater than 3.3-fold compared with the previous dose. The maximum dose of ABI-4334 to be evaluated in Part A (SAD) will not exceed the exposures observed in dogs at the NOEL dose of 30 mg/kg/day, or 1000 mg/day, whichever is lower.

Figure 2. Study Design Schematic – Part A (SAD in Healthy Subjects)

Abbreviations: DRC=Data Review Committee; PBO=placebo; SAD=single ascending dose

Each of the Cohorts A1-A5 will enroll 8 healthy subjects who will be randomized in a 6:2 ratio to receive a single oral dose of the study drug, ie, ABI-4334 (6 subjects) or PBO (2 subjects) in a fasted state, followed by a 7-day follow-up period. Subjects will remain confined to the study clinic from Days -1 to 4, with outpatient follow-up visits, as specified in [Appendix 1](#). Dosing of a subsequent SAD cohort can begin at least 8 days after dosing of the sentinel subjects from the previous cohort (see below).

Because this is a FIH study, a sentinel dosing approach will be utilized for each Cohort A1-A5, where initially only 2 subjects per cohort will be dosed (one receiving ABI-4334 and one receiving PBO). These sentinel subjects will be observed for a minimum of 3 days postdose to ensure acceptable tolerability of the study drug, as determined by the DRC, before dosing of the remaining subjects within the cohort can proceed.

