4.1.2 Part B (MAD in Healthy Subjects)

[figure not shown]
Part B dosing may commence prior to Part A being completed. The dose level and dosing schedule for the first cohort of Part B, ie, Cohort B1, will be determined based on emergent safety, tolerability, and PK data from completed Part A cohorts, with the daily dose at least 2-fold lower than a Part A dose level deemed safe and tolerable.

Both cohorts planned for Part B, ie, Cohort B1 and Cohort B2, will enroll 8 healthy subjects who will be randomized in a 6:2 ratio to receive oral daily doses of the study drug, ie, ABI-4334 (6 subjects) or PBO (2 subjects), for 8 consecutive days, followed by a 7-day follow-up period ([Figure 3](#)). Dosing may occur under fasted or fed conditions, depending on the results from the food-effect cohorts in Part A. Subjects will remain confined to the study site from Days -1 to Day 11 (ie, 3 days post last day of dosing), with outpatient follow-up visits, as specified in [Appendix 2](#).

The dose level and dosing schedule for Cohort B2 will be based on an evaluation by the DRC of safety data from Day 1 through Day 8 for Cohort B1 and all available safety data for preceding cohorts. In addition, PK data through 24 hours after dosing on Day 8 for Cohort B1 and available PK data for preceding cohorts will be reviewed. In no case would the dose escalation be greater than 3.3-fold compared with the previous dose. Dosing of Cohort B2 can begin at least 11 days after the first day dosing of subjects in Cohort B1. The maximum dose of ABI-4334 to be evaluated in Part B (MAD) will not exceed the exposures observed in dogs at the NOEL dose of 30 mg/kg/day, or 1000 mg/day, whichever is lower.

Details on PK sampling for Part B (MAD) are provided in [Section 8.4](#) and [Appendix 2](#).

Figure 3. Study Design Schematic – Part B (MAD in Healthy Subjects)

Abbreviations: DRC=Data Review Committee; PBO=placebo

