10 STATISTICAL CONSIDERATIONS

10.1 General Considerations

This section provides the key details of the statistical analyses to be performed using data captured according to this protocol. A complete Statistical Analysis Plan (SAP) describing all planned analyses will be finalized prior to database lock. For all analyses, Baseline will be defined as predose, Day 1 or Screening closest to Day 1 (predose) if Day 1 testing is not available.

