Note: When multiple procedures are scheduled at the same time, the order of events will be: Holter extraction, followed by 12-lead ECGs, vital signs, PK blood sample collection (to be collected on the scheduled time point), and meals. The only exception will be at 2 and 4 hours postdose, when the 12-lead ECG will be performed before the Holter extraction

- ^a Collection of vital signs and ECG will be repeated throughout the day. Specifically, vital signs will be collected predose (within 2 hours before dosing) on Day 1, and at 2, 4, 8, 12, 24, 48, 72, 96, 120, and 144 hours after dosing on Day 1. Collection of ECG will be performed predose on Day 1, and at 2, 4, 12, and 24 hours (ie, Day 2) after dosing on Day 1; and anytime on Days 4 and 7. The window for collection of vital signs and ECGs will be ± 15 minutes.
- ^b Holter data collection timepoints on Day 1 are -60, -45, and -30 minutes predose and 0.5, 1, 2, 3, 4, 5, 6, 9, 12, 18, and 24 hours (ie, Day 2) postdose (time matched to PK assessments). Holter monitoring will not be performed for Cohort A7.
- ^c Only for female subjects < 54 years of age with no spontaneous menses for > 12 months.
- ^d A serum pregnancy test is required at Screening and Day -1 for female subjects of childbearing potential. On Day 1, a urine pregnancy test will be performed for females of childbearing potential, prior to dosing. All post Day 1 pregnancy tests may be conducted by urine dipstick. If positive on dipstick, reflex to serum.
- ^e For antibody tests, if antibody is positive, reflex to DNA or RNA (as applicable).
- ^f On Day 1, samples for clinical laboratory tests will be taken predose.
- ^g Blood samples for PK analysis of ABI-4334 in plasma will be collected at the following time points: predose (within 0.5 hours before dosing) and 0.5, 1, 2, 3, 4, 5, 6, 9, 12, 18, 24, 36, 48, 72, 96, 120, and 144 hours after dosing on Day 1; Time point windows are ± 2 minutes for 0.5- and 1-hour postdose samples and ± 5 minutes for samples from 2 through 18 hours postdose and ± 30 minutes for samples 24 hours postdose and after.
- ^h A complete physical exam will be done before the subject is discharged from the study site.

APPENDIX 1b. SCHEDULE OF ASSESSMENTS FOR SCHEDULED VISITS: PART A – SAD (COHORT A6, COHORT A7 Period 2)

Period of Visit Study Day	Treatment		Follow-Up					
	Day -1	Day 1 (LDD)	Day 2	Day 3	Day 4	Day 5	Day 6	Day 7 (EOS)
Visit Windows (days)	NA	NA	NA	NA	NA	NA	NA	NA
In-Clinic Assessments								

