3.5.4 Definition of Baseline

For all analyses, Baseline will be defined as the last non-missing evaluation prior to the first dose date/time. For cohort A7, Period 2 Baseline will be defined as last non-missing evaluation prior to the dosing on Period 2 Study Day 1.

For all cohorts, except cohort A7 Period 2, Change from Baseline will be defined as the result at desired timepoint minus the result at Baseline. For cohort A7 Period 2, Change from Baseline will be defined as the result at desired timepoint minus the result at Period 2 Baseline.

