5.2.1.1 Treatment-Emergent Laboratory Abnormalities

Treatment-emergent laboratory abnormalities will be defined as values that increase at least 1 toxicity grade from Baseline at any post-Baseline time point. If the relevant Baseline laboratory value is missing, any abnormality of at least Grade 1 observed within the time frame specified above will be considered treatment emergent.

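### No exercise rule covers the days before the Baseline chemistry samples, so recent unusual exercise may raise Baseline creatine kinase, AST and ALT in some subjects

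*Combined protocol and SAP*

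**What the plan says.** The exercise rule in protocol Section 5.5 reads: "Subjects will not engage in strenuous exercise beyond their accustomed daily level of activity from Day 1 dosing through end of study". It limits only strenuous activity above what the subject is used to, and it takes effect at dosing.

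Other rules in that list begin sooner. For alcohol: "Subjects are prohibited from consuming any amount of alcohol 48 hours before dosing on Day 1 through end of study". Caffeine has the same 48-hour lead, grapefruit and related fruit have 7 days, and nicotine is barred from Screening.

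The reference sample comes before dosing. Protocol Section 10.1: "Baseline will be defined as predose, Day 1 or Screening closest to Day 1 (predose) if Day 1 testing is not available". SAP Section 3.5.4: "Baseline will be defined as the last non-missing evaluation prior to the first dose date/time". The Part A schedule (Appendix 1a, footnote f) adds: "On Day 1, samples for clinical laboratory tests will be taken predose".

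SAP Section 5.2.1.1 defines treatment-emergent laboratory abnormalities as "values that increase at least 1 toxicity grade from Baseline at any post-Baseline time point". SAP Section 5.2.3 summarises change from Baseline at each visit. Creatine kinase, ALT, AST and LDH are all in the chemistry panel (protocol Table 2).

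Subjects are admitted the day before dosing. Part A: "Subjects will remain confined to the study clinic from Days -1 to 4". Part B: "Subjects will remain confined to the study site from Days -1 to Day 11".

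**The concern.** The exercise condition is controlled for the samples that follow dosing but not for the sample they are compared with. If unusual exertion before admission lifts a subject's enzymes, Baseline is too high for that subject and later values drift down whatever the drug does. Inclusion criterion 5 accepts out-of-range values that the investigator judges not clinically significant, so a raised value need not exclude the subject.

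At stake are the change-from-Baseline and treatment-emergent tables for the muscle and liver enzymes in a first-in-human study. Abnormal laboratory results are part of the primary endpoint, tables are by cohort and treatment, and each randomised cohort has 6 active and 2 placebo subjects. One affected subject can be visible in the summary.

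**Working it through.** The plan states no figure on this point, so there is none to reproduce. The check is of timing, then of the grading arithmetic. All enzyme levels and half-lives below are assumptions, because the documents give none.

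**1. Timing**

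| Interval | Written exercise rule | Setting |
|---|---|---|
| Before Day -1 | none | at home |
| Day -1 to predose Day 1 (Baseline) | none | confined, about one day or less |
| Part A Days 2 and 3; Part B Days 2 to 8 | in force | confined |
| Part A Days 5 and 7; Part B 7 days after last dose | in force | outpatient, accustomed exercise allowed |

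The gap is therefore the days before admission. Appendix 2 has no predose footnote on the Part B Day 1 chemistry. If that sample were not predose, Baseline would fall back to Day -1 or Screening, with less or no confinement before it.

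**2. Treatment-emergent threshold (Appendix 4 cut-offs with the one-grade rule)**

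- Creatine kinase: Grade 1 is 3 to <6 x ULN. From an ungraded Baseline the flag appears at 3 x ULN; from a Grade 1 Baseline, at 6 x ULN.
- ALT and AST: Grade 1 is 1.25 to <2.5 x ULN. The flag moves from 1.25 to 2.5 x ULN.
- LDH is not graded in Appendix 4, so only its change from Baseline can be affected.

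Example for a postdose creatine kinase of 4 x ULN:

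| Baseline (x ULN) | Flagged? | Change (x ULN) |
|---|---|---|
| 1 | yes | 4 - 1 = +3 |
| 2 | yes | 4 - 2 = +2 |
| 2.9 | yes | 4 - 2.9 = +1.1 |
| 3 | no | 4 - 3 = +1 |

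For ALT, a postdose 2.4 x ULN is flagged from a Baseline of 1.2 but not from 1.3.

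**3. Mean change in a group of 6**

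Assume a level L (x ULN) 48 h before dosing, with the excess over 1 x ULN halving every h hours:

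- Baseline = 1 + (L - 1) x 0.5^(48/h)
- Day 7 (144 h postdose) = 1 + (L - 1) x 0.5^(192/h)
- Shift in the group mean from one affected subject = (Day 7 - Baseline)/6

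| L | h | Baseline | Day 7 | Shift |
|---|---|---|---|---|
| 10 | 24 | 3.25 | 1.04 | -0.37 |
| 10 | 36 | 4.57 | 1.22 | -0.56 |
| 10 | 48 | 5.50 | 1.56 | -0.66 |
| 3 | 24 | 1.50 | 1.01 | -0.08 |
| 3 | 48 | 2.00 | 1.13 | -0.15 |

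Baseline reaches Grade 1 (3 x ULN) only if L is at least 1 + 2/0.5^(48/h), which is 9 for h = 24 and 5 for h = 48. The L = 10 rows are an extreme; the L = 3 rows lose no flag.

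**4. Placebo contrast**

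Randomised placebo subjects share the shift on average. The standard error of an active-minus-placebo difference, in SD units, is sqrt(1/6 + 1/2) = 0.82 within a cohort. It would be sqrt(1/6 + 1/10) = 0.52 against 10 pooled Part A placebo subjects and sqrt(1/6 + 1/4) = 0.65 against 4 in Part B. The SAP states no pooling.

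**5. What an earlier start would achieve**

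A 48-hour lead before Day -1 is about 72 h before dosing. With L = 10 at that point, Baseline = 1 + 9 x 0.5^(72/h) = 2.1, 3.25 and 4.2 x ULN for h = 24, 36 and 48. The carry-over is smaller than in step 3 but is not removed.

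**The case against.** A reader might infer that Baseline is taken under free exercise and every later value under restriction, so that a drug-related rise is systematically hidden. The documents do not support that. The Part A Baseline follows a night in the clinic, accustomed exercise stays permitted after dosing, and confinement accounts for much of the difference in conditions.

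Further points against the concern stand:

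- Nothing in the documents links exercise to these enzymes or shows that an effect would last until the Day 1 sample. That step is an assumption.
- SAP Section 5.2.1.2 tabulates maximum postbaseline grade, and the listings in SAP Section 5.2 flag out-of-range or graded values. Neither needs Baseline. Observed values are also summarised by visit.
- Cohort stopping criteria (protocol Section 7.2) and the Data Review Committee's safety triggers (Section 10.6.2) do not use change from Baseline.
- In the main cohorts chemistry is also drawn at Screening and Day -1, so an odd Baseline can be seen against earlier values.
- Mean change from Baseline is not itself part of the primary endpoint.
- Placebo shares the shift, so an active-versus-placebo comparison gains noise rather than expected bias.

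These points limit the harm but do not close the gap. Confinement does not reach exercise before admission, two placebo subjects per cohort cannot reliably correct for one affected subject, and the treatment-emergent and change tables still depend on Baseline.

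**Conclusion.** The point holds as a minor, cheap improvement. No exercise rule covers the days before the reference chemistry, and the SAP relies on that reference for two sets of tables. The threshold effect is exact where it applies, but it applies only to a subject whose Baseline is already Grade 1 or higher. Below that, only the change shrinks.

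Size and frequency are unknown. Under the assumed decay, one affected subject moves a six-subject mean creatine kinase change by about -0.1 to -0.7 x ULN, and the upper end needs an extreme starting level. It would go too far to conclude that the active-versus-placebo comparison is biased or that safety signals will be missed.

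Cohort A6 deserves its own mention. Appendix 1a labels Day 7 of the fasted cohort as end of study, where the rule lapses. The washout has a minimum but no maximum, and Appendix 1b has no Day -1 chemistry. The point there assumes that the A6 predose sample serves as its reference, as protocol Section 4.1.1 implies. Cohort A7 Period 2 needs no change: SAP Section 3.5.2.2 places end of study after Period 2, so its Baseline is already under the rule.

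**What to change.** In protocol Section 5.5, start the exercise restriction before the Day -1 chemistry sample, with at least the 48-hour lead already used for alcohol and caffeine. A longer lead would reduce carry-over further. State separately that the same restriction applies before admission to Cohort A6.

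The cost is one line in the protocol and the matching line in the subject instructions. Subjects accept a few more days of a mild restriction. No analysis, sample or visit changes.
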